1.5.10 Rationale for Secondary Outcome Measure: Safety

The combination of HPV peptides and Candin® was first tested in the Phase I clinical trial, and appears to be safe as no DLTs have been reported (Table 2). Safety will be assessed in the same manner in the Phase II clinical trial using CTCAE 4.03.

1.5.11 Rationale for Tertiary Outcome Measures: Immunological Response and Viral Clearance

1.5.11.1 Rationale for Measuring HPV-specific T-Cell Response

HPV-specific CD3 T-cell responses will be assessed using immune assay such as the IFN- γ ELISPOT assay before vaccination, after 2 vaccinations, 6 months after 4 vaccinations, and 12 months after 4 vaccinations (Fig. 6). In order to evaluate the role of CD3 T-cells in vaccine efficacy, whether clinical response and viral clearance can be predicted based on the CD3 T-cell activities will be assessed.

1.5.11.2 Rationale for Measuring Circulating Immune Cells

The level of circulating immune cells, including Th1 cells, Th2 cells, regulatory T-cells (Treg), and myeloid-derived suppressor cells (MDSC), will be assessed before vaccination, after 2 vaccinations, 6 months after 4 vaccinations, and 12 months after 4 vaccinations. The data from the Phase I clinical trial indicated that PepCan may increase Th1 responses ($p=0.02$) and decrease Th2

responses resulting in increased effector immune activity (**Fig. 4**). Whether the levels of these circulating immune cells can be used to predict vaccine efficacy in terms of clinical response and viral clearance will be investigated. Vaccine effects on these factors will also be examined throughout the study (i.e., 6 and 12 months instead of 3 months).

1.5.11.3 Rationale for Measuring Viral Clearance

HPV-DNA testing will be performed at the Screening Visit, 6-Month Visit, and 12-Month Visit (**Fig. 6**). In the Phase II study, an HPV type would be considered to be cleared if it is present at the Screening Visit but not at the 6-Month and 12-Month Visits.

1.5.12 Rationale of Other Outcome Measures: Predicting Vaccine Response Using Various Factors Such as Age, Oral Contraceptive Use, Smoking History, Circulating Immune Cells, HLA Types, HPV Types, Cytokine/Chemokine, and Metabolomic Profiling; Evaluating Vaccine Effect; Determining Cross-Protection and Examining Epitope-Spreading and Cross-Reactivity as Possible Mechanisms

Not all vaccine recipients are expected to have clinical response. Some may have persistent HSIL, and some may progress to invasive squamous cell carcinoma. It would be valuable to identify factors that are associated with a favorable response so an educated decision can be made as to who should receive the vaccine.

The Phase I clinical trial has indicated that PepCan is effective in HSILs with HPV 16 and non-16 HPV types. In the Phase II clinical trial, against which non-16 HPV types it is effective may be determined. Furthermore, epitope spreading and cross-reactivity may be investigated as possible mechanisms behind cross-protection.

1.5.13 Rationale for Adding a Candin® Arm

The results of the dose-escalation portion of the Phase I clinical trial showed similar rates of clinical responses in subjects with HSILs associated (4 of 9 or 44%) and not associated (8 of 14 or 57%) with HPV 16 suggesting that *de novo* immune stimulation presumably from Candin® plays a major role. Therefore, Candin® only treatment arm will be added to compare efficacy between PepCan and Candin®.

1.5.14 Rationale for Randomization and Double-Blinding

In order to minimize bias, subjects who are eligible for vaccination will be randomly assigned to one of the two treatment arms (PepCan or Candin®) in a double-blinded fashion so the subjects and study staff (except for pharmacy staff) will not know which treatment is being administered. PepCan and Candin® are both clear solutions prepared in the same 1 mL syringe.

1.6 POTENTIAL BENEFITS AND RISKS TO SUBJECTS

1.6.1 Potential Benefits

The intended benefit is global with the development of a novel HPV therapeutic vaccine for treatment of HSIL preventing the development of cervical cancer. This study will contribute to this goal by evaluating the efficacy and safety of a version of HPV therapeutic vaccine, PepCan. It is not known whether a particular study subject will benefit, as it is not possible to predict which subjects will qualify for vaccination and of those vaccinated, who will achieve clinical response. However, a subset of subjects who qualify for vaccinations are expected to show clinical response enabling them to avoid a surgical treatment such as LEEP. This would be particularly beneficial to those who plan to conceive after study participation.

1.6.2 Risks of PepCan

No DLTs were observed in the phase I trial (**Table 2**). However, the total number of individuals who have received the vaccine is small, and there may be relatively rare complications that have not surfaced. The most commonly reported side effects were local swelling, redness, increased skin temperature, and local pain at injection sites.

1.6.3 Strategies to Minimize Risks

All subjects will be screened before enrollment. Thereafter, a pregnancy test will be performed prior to each vaccination, and they will be asked to stay in the clinic for a minimum of 30 min after each injection. To ameliorate possible and anticipated localized minor vaccination site reactions, subjects will be offered a dose of ibuprofen or naproxen after the 30 min observation period. It is generally recommended to start with the lowest dose of these medications after experiencing a prior injection site reaction. However, any dose available can be given.

1.6.4 Strategies to Minimize Bias

The subjects who are eligible for vaccination will be randomized to two treatment groups (PepCan and Candida) at a 1:1 ratio in a double-blinded fashion. A computer generated randomization scheme will be created by a study statistician, which will assign subjects to one of the treatment groups based on the order of first vaccination dates. This information will be forwarded to research pharmacy. A subject will be vaccinated with the same agent for all 4 vaccinations. After the subject completes her 12-Month Visit, a study coordinator will obtain information on which treatment she received from the research pharmacy, and will inform the subject, so she can make informed decisions about her future treatment plans. For a subject who exits the study early for any reason, the treatment she received will be revealed after completing the Early Termination Questionnaire.

2 OBJECTIVES

2.1 PRIMARY OBJECTIVE: EFFICACY

To assess the efficacy of PepCan and Candin® in a Phase II clinical trial by determining clinical response which will be assessed by obtaining colposcopy-guided quadrant biopsies at the 12-Month Visit. Responses will be compared between (1) the PepCan group and a historical placebo group [57], (2) the Candin® group and the same historical placebo group, and (3) the PepCan and Candin® groups. If, upon the 12-Month Visit quadrant biopsies, a subject does not have any evidence of CIN, she would be considered a “complete responder”. If the lesion(s) has(have) regressed to CIN 1, the subject will be considered to be a “partial responder”. If there is still CIN 2 and/or 3 present at the 12-Month Visit, the subject will be considered a “non-responder”. The highest grade among the biopsies will be recorded. In addition to the above analysis of subjects who exited after the 12-Month Visit, another analysis may be performed with addition of subjects who exited the study after the 6-Month Visit if histological results (biopsy and/or LEEP) are available at 6 months.

2.2 SECONDARY OBJECTIVE: SAFETY

Safety will be assessed by documenting AEs from the time of enrollment until the 12-Month Visit according to CTCAE v4.03.

2.3 TERTIARY OBJECTIVES: IMMUNOLOGICAL RESPONSE & VIRAL CLEARANCE

Immunological assessment in terms of HPV-specific CD3 T-cell responses will be assessed using an IFN- γ ELISPOT assay while circulating levels of CD4, Th1, Th2, Treg, and MDSC cells will be assessed by FACS analysis before vaccination, after 2 vaccinations, 6 months after 4 vaccinations, and 12 months after 4 vaccinations. Virological assessments will be made at Screening, 6-Month, and 12-Month Visits.

2.4 OTHER OBJECTIVES

To evaluate predictive factors for response to PepCan or Candin®, various parameters such as age, oral contraceptive use, smoking history, circulating immune cells, HLA types, HPV types, bacterial taxa, cytokine/chemokine, metabolomic profiling, and other factors may be analyzed. Vaccine effects over time on some of these factors will also be assessed.

Cross-protection by PepCan in terms of viral clearance will be determined by tallying each HPV event that is present at Screening Visit but becomes undetectable at both 6-Month and 12-Month Visits for each of the 37 HPV types tested. Viral clearance by *de novo* immune stimulation by Candin® will be determined by tallying each HPV event that is present at Screening Visit but becomes undetectable at both 6-Month and 12-Month Visits for each of the 37 HPV types tested.

Epitope spreading and cross-reactivity may be examined in selected subjects in the PepCan arm.

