Our group has developed a vaccine consisting of four clinical good manufacturing practice (cGMP) grade synthetic peptides covering the HPV type 16 E6 protein and *Candida* skin test reagent as a novel vaccine adjuvant (named PepCan). The dose-escalation portion of the Phase I clinical trial of the therapeutic vaccine treating women with biopsy-confirmed HSILs has recently been completed (the final dose phase using the clinically optimal dose of 50 μ g per peptide is still ongoing). No dose-limiting toxicities (DLTs) [vaccine-related allergic and autoimmune adverse events (AEs) > Grade 1 and any other AEs > 2 Grade 2] have been observed. The highest % of histological regression was observed in the lowest dose (50 μ g per peptide) group (5 of 6 or 83%) with the overall (50, 100, 250, and 500 μ g per peptide doses were tested) response rate of 52% (12 of 23). Both these rates are above that of a historical placebo group of 22% [16]. Both subjects with HPV 16 and non-16 HPV-positive HSILs responded to PepCan. While we are assessing histological response 3 months after vaccination, the full effect takes 1 year [17-19] to manifest as demonstrated by increase in histological regression from 25% to 47% of vulvar intraepithelial lesions treated by a similar vaccine [18].

This phase II clinical trial aims to assess the full clinical efficacy of PepCan by assessing response at 1 year, to identify factors, which can predict favorable vaccine response, examine vaccine effects, and to define against which non-16 HPV types this vaccine is effective. Candin® alone will also be examined. Approximately 125 subjects will be screened and 80 subjects will be vaccinated over 3.5 to 4.5 years. If needed additional year can be added.

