1.3 SCIENTIFIC RATIONALE

1.3.1 Rationale for Using HPV Peptides as the Antigen

1.3.1.1 Importance of the T-Cell Responses to HPV 16 E6 Protein in Viral Clearance

The National Cancer Institute (NCI)-supported study conducted by [name], was one of the first to describe the relationship between viral persistence and development of SILs [20-22]. Women were recruited at the San Francisco State University Medical Clinic and the Hayward Planned Parenthood Clinic. A total of 654 women were actively followed via clinic visits every 4 months. At these visits, a sexual-history interview, Pap smear, colposcopy, and HPV-deoxyribonucleic acid (DNA) testing on cervical lavage specimens were performed. [name], PhD [principal investigator (PI)], first studied T-cell immunity against HPV in this cohort.

HPV 16 E6- and E7-specific cytotoxic T lymphocytes (CTLs) were demonstrated in subjects who had evidence of HPV 16 infections but had not developed SILs [23-25]. In a small cross-sectional study, the percentage of subjects who demonstrated HPV 16 E6- and/or E7-specific CTLs was higher in the group of women with HPV 16 infections without SILs than in the group of women with HPV 16 infections who developed SILs [23].

In women with polymerase chain reaction (PCR)-detected cervical HPV 16 infections (from the same cohort described above), we examined the association between HPV 16 E6- and E7-specific CTLs and HPV 16 persistence, using a longitudinal study design involving multiple CTL assays [25]. Women with HPV 16 infections (n=51) were enrolled, along with women who were HPV 16 negative as controls (n=3). Twenty-two of 40 (55%) women whose HPV 16 infections had cleared each had at least one E6 CTL response, while none of the nine women who had HPV 16 persistence had such a response ($p=.003$). This difference was not demonstrated for E7; 25 of 40 (63%) women whose HPV 16 infections cleared had E7 CTL responses, and five of nine (56%) women with persistent infections had responses ($p=.720$). Therefore, **the CTL response to E6 appears to be important in clearing HPV 16 infection**. We also examined whether these T-cells were CD4- and/or CD8-positive using antibody blocking and T-cell subset separation experiments, and we demonstrated that both CD4- and CD8-positive T-lymphocytes demonstrated anti-HPV activities [24].

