In a subsequent study (same cohort) with the same design, we found similar results using *ex vivo* interferon (IFN)- γ enzyme-linked immunospot (ELISPOT) assays instead of CTL assays [26]. Fourteen of 24 (58%) women whose HPV 16 infections cleared each had an E6 response at least once, while none of 10 (0%) women who had HPV 16 persistence had a response ($p=.002$). For E7, 8 of 24 (33%) women whose HPV 16 infections cleared each had an E7 CTL response, and none of 10 (0%) women with persistence had such a response ($p=.04$). These results confirmed the importance of T-cell responses to E6 and indicated that E7 may also play a role.

1.3.1.2 Importance of the CD8 and CD4 T-Cell Responses to HPV 16 E6 in Regression of Cervical Lesions

[figure not shown]
Eighty-five subjects with recent histories of untreated abnormal Pap smears were recruited from the University of Arkansas for Medical Sciences (UAMS) Obstetrics and Gynecology Clinics between 1/11/07 and 7/15/08. HPV-DNA tests using the Linear Array HPV Genotyping Test (Roche Diagnostics, Indianapolis, IN) and ELISPOT assays using the HPV 16 antigens were performed on cervical cytology specimens (ThinPrep, Cytoc Corporation, Marlborough, MA) [27, 28]. From whole-blood-derived peripheral blood mononuclear cells (PBMCs), CD8 T-cell lines were established by two rounds of *in vitro* stimulation of magnetically selected CD8 T-cells with autologous mature DCs infected with recombinant vaccinia viruses expressing E6 or E7 (E6-vac

or E7-vac), and the pattern of immunodominance was examined with ELISPOT assays using 15-mer peptides that overlap by 10 amino acids [28]. Evidence of potential antigenic epitopes was defined by spot-forming units greater than twice the amount for the no-peptide control. The subjects with subsequent normal histological diagnoses were considered to be regressors (n=28) while those with histological diagnoses of CIN 1, 2, or 3 were considered to be persistors (n=37). The indeterminate group included subjects (n=20) for whom diagnoses were equivocal (such as atypical squamous cells of undetermined significance but not excluding HSIL) or for whom insufficient samples were submitted.

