1.5 RATIONALE FOR PHASE II CLINICAL TRIAL

1.5.1 Need for HPV Therapeutic Vaccines

Although numerous preclinical and clinical trials have evaluated prophylactic HPV vaccines during the past few decades, these vaccines do not help those who already have established HPV infections [51]. Gardasil, a quadrivalent HPV L1 virus-like particle prophylactic vaccine (HPV types 16, 18, 6, and 11), was the first to be FDA-approved in 2006; a bivalent version (HPV types 16 and 18), Cervarix, was approved by the FDA three years later. Clinical trials have demonstrated excellent vaccine efficacy in women negative for HPV 16 or HPV 18[52, 53], but the duration of protection remains to be determined, and a study of the bivalent vaccine showed no evidence of enhanced viral clearance in women with pre-existing HPV infections (n=1,259; 35.5% clearance in vaccinated group, 31.5% in a group receiving a negative control vaccine, $p=NS$) [51]. Therefore, therapeutic vaccines are needed for cases in which HPV infection is already established and in which HPV-related diseases have already developed. This is the particularly true because the prophylactic vaccine coverage rate in the targeted group (girls aged 13–17 years) has been reported to be only 32% nationally [54]. Although the standard surgical treatments for HSILs such as LEEP are very effective [14], their unintended side effect of increased incidence of preterm delivery from 4.4% to 8.9% [14, 15] has become a concern. Henceforth, the latest guideline no longer recommends treatment for CIN2 in young women (narrowly defined as ≤ 24 years old and broadly defined as any women who still plans to become pregnant [14]). Treatment is still recommended for CIN3 but observation is now considered acceptable. A new treatment, which does not alter the anatomical integrity of the cervix like the HPV therapeutic vaccine, is very much needed. In short, **HPV therapeutic vaccines are needed** because (1) prophylactic vaccines are not effective against established HPV infection, (2) utilization of the prophylactic vaccines has been low, (3) therapeutic vaccines would leave the cervix intact and would likely not increase the risk of preterm deliveries, and (4) therapeutic vaccine maybe effective against other cancers caused by HPV such as anal, oropharyngeal, penile, vaginal, and vulvar cancers.

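### Cross-protection by PepCan is judged from a single-arm count of HPV types that disappear; without a planned between-arm contrast, that count cannot separate a PepCan effect from natural or Candin-driven clearance.

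*Protocol*

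**What the plan says.** Section 2.4 of the protocol (Other Objectives) gives the method in one sentence: "Cross-protection by PepCan in terms of viral clearance will be determined by tallying each HPV event" that is present at screening and "becomes undetectable at both 6-Month and 12-Month Visits for each of the 37 HPV types tested". The next sentence applies the same rule to the other arm under a different causal label: clearance by de novo "immune stimulation by Candin® will be determined by tallying each HPV event that is present at Screening Visit" and later lost.

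The purpose is stated twice. Section 1.2 lists among the trial's aims "to define against which non-16 HPV types this vaccine is effective". Section 1.5.12 is more tentative: "against which non-16 HPV types it is effective may be determined".

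No other section compares clearance between arms:

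- Sections 2.1 and 9.1, and SAP section II, compare histological response only.
- Section 9.3.2 relates clearance to clinical response by Fisher's exact test, within each arm separately.
- Section 9.3.1.1 does compare the arms, to isolate what the peptides add, but only on T-cell regions.
- Section 9.5 covers predictors of response and viral clearance and does not name treatment arm as a variable.
- The SAP covers baseline characteristics, efficacy and safety, and has no virological analysis.

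**The concern.** HPV infections also clear without treatment. Section 1.5.1 of the protocol reports, for women with existing infection, "35.5% clearance in vaccinated group, 31.5% in a group receiving a negative control vaccine". A count in one arm has no denominator, no expected value and no comparator, so it cannot say how many of the cleared types would have cleared anyway.

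The second difficulty comes from the design rationale. Section 1.5.13 adds the Candin arm because lesions with and without HPV 16 responded at similar rates in Phase I (4 of 9 and 8 of 14), which the authors attribute largely to Candin. On that hypothesis, a non-16 infection that clears on PepCan may be a Candin effect. Counting it as cross-protection by PepCan sets aside the reason for having two arms.

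At stake is a statement about which non-16 types PepCan works against. Followed as written, the method would attach that statement to clearance from any cause.

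**Working it through.** **The plan's own figure.** The documents give no power, sample size or expected count for viral clearance or cross-protection. The 91% power in section 1.5.9 concerns histology (60% against 34 of 117, 35 women on PepCan). A two-sample normal approximation returns 91.6%, so that figure reproduces, but it says nothing about clearance.

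**Step 1: expected count with no vaccine effect.** Formula: expected cleared events = clearance rate × baseline infections.

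- Infections per arm (assumed; the documents give none): from 35 (35 completers × 1 type) to 80 (40 enrolled × 2 types).
- Clearance rate: 31.5% is borrowed from section 1.5.1; 20% and 50% are assumptions to show the range.

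| Clearance rate | 35 infections | 80 infections |
|---|---|---|
| 20% | 0.20 × 35 = 7 | 0.20 × 80 = 16 |
| 31.5% | 0.315 × 35 = 11.0 | 0.315 × 80 = 25.2 |
| 50% | 0.50 × 35 = 17.5 | 0.50 × 80 = 40 |

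**Step 2: a single rare type.** If three women in an arm carry a type, the chance that at least one clears it with no effect is 1 − (1 − q)³: 49% at q = 20%, 68% at 31.5% and 88% at 50%. A non-zero count for a type is therefore unremarkable. The three carriers are an assumption.

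**Step 3: what a between-arm contrast could deliver.** Power of Fisher's exact test, two-sided 0.05, with 31.5% on Candin and assumed rates on PepCan, one infection per woman:

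| Infected women per arm | 31.5% vs 60% | 31.5% vs 70% |
|---|---|---|
| 35 | 57% | 85% |
| 20 | 31% | 56% |
| 10 | 11% | 22% |
| 5 | 8% | 14% |
| 3 | 0% | 0% |

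Precision tells the same story. If both arms clear 31.5%, the approximate 95% half-width is 1.96 × √(2 × 0.315 × 0.685 / n): 22 percentage points at n = 35 and 14 at n = 80. The second value ignores correlation between types in the same woman and counts every infection as non-16, so it is optimistic. Testing the 36 non-16 types separately at 0.05 would carry a family-wise error of up to 1 − 0.95³⁶ = 84% if the tests were independent. The realistic primary contrast is one pooled over non-16 types.

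**Step 4: can the existing groups be used?** Section 8.2 tests 37 types. It lists 6 as HPV 16-related, 13 as high-risk and 13 as low-risk; with HPV 16 itself that is 33. Types 26, 55, 64 and IS39 belong to no group (37 − 33 = 4).

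**The case against.** Several points on the other side stand:

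- The Candin arm is counted by the identical rule, and allocation is 1:1 and double-blind. The data for a contrast will exist; what is missing is the contrast. A reader might infer that cross-protection has no comparator at all, which goes too far.
- Requiring a negative result at both visits reduces false clearance from test variability. It does not remove natural clearance.
- Epitope spreading and cross-reactivity may be studied as supporting evidence. They address mechanism and do not supply the missing comparison.
- The objective ranks below primary, secondary and tertiary, and section 1.5.12 is cautious. Section 2.4, however, says how cross-protection will be determined, so this is a stated method and more than a missing detail.

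The 31.5% is a weak transfer. Section 1.5.1 gives no time window, clearance definition or unit of analysis, and the women were not selected for biopsy-proven HSIL. The cohort studies in section 1.3.1.1 (40 women who cleared HPV 16 against 9 with persistence; 24 against 10) report group sizes in immunology studies, not designed estimates of a clearance rate. They show that clearance without a therapeutic vaccine is not rare, and no more.

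A reader might also want the probability that some type would be wrongly named as cross-protected. The plan contains no rule for naming a type, so any such probability would rest on an invented threshold.

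**Conclusion.** The concern holds as stated in the heading. Section 2.4 draws a causal conclusion from a single-arm count, and no section compares clearance between arms. With no vaccine effect the count could plausibly be anywhere from about 7 to 40 events, depending on an assumed 35 to 80 infections and an assumed 20% to 50% clearance. The range illustrates the problem and does not predict this trial's count; the conclusion does not depend on any one rate.

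Two stronger readings are not supported. The first is that the trial's efficacy conclusion is compromised: the primary comparisons are histological and do not use the count. The second is that comparing PepCan with Candin would recover PepCan's full effect over natural history. There is no untreated arm and Candin is regarded as active, so that contrast isolates only what the E6 peptides add. The point is worth correcting because the aim is stated and the data are already collected.

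**What to change.** In protocol sections 2.4 and 9.3.2, and in a virology section added to the SAP:

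1. Report cleared over baseline infections by arm, keeping the two-visit definition.
2. Estimate the PepCan minus Candin difference in clearance of non-16 infections with a 95% confidence interval that allows for several types per woman, for example by a cluster bootstrap that resamples women. Present it pooled first, then by the section 8.2 groups.
3. Assign types 26, 55, 64 and IS39 to a stated group. Report HPV 16 separately, since its clearance is not cross-protection.
4. Describe the contrast as the added effect of the E6 peptides over Candin, and state that a null contrast does not exclude Candin-driven clearance of non-16 types.
5. Label single-arm and per-type counts descriptive.

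If clearance by arm has already been seen, say that the contrast was specified afterwards.

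The cost is a short addition to the text and one further analysis of data already collected. The downside is modest precision: few or no individual types will support a claim, and the pooled interval may be too wide to settle the question.
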